**Multicentre Randomised Controlled Trial of
Compression Therapy following Endovenous Thermal
Ablation of Varicose Veins**

FULL TITLE

A multicentre randomised controlled trial of compression therapy following endovenous thermal ablation of varicose veins.

SUMMARY

This study will be looking at the effect of compression therapy in patients having endovenous treatment for truncal incompetence of their varicose veins using either radiofrequency ablation (RFA) or endovenous laser therapy (EVLT). Patients will be randomised to either the compression group (group A) or the no compression group (group B).

The pain scores, compliance, quality of life scores, occlusion rate at 6 months as well as the cost effectiveness of each intervention will be assessed.

OBJECTIVES

- Primary Objective

Patient's pain score for the first 10 days post-procedure using the visual analogue scale (VAS)

- Secondary Objective

The secondary objectives would be to compare the two treatment groups with respect to:

- The quality of life scores at baseline, 2 weeks and 6 months using the EQ-5D, AVVQ and CIVIQ scores
- The clinical change using the VCSS at baseline, 2 weeks and 6 months
- The degree of bruising and phlebitis at 2 weeks and 6 months
- The patient compliance with the intervention
- The time taken to return to work and normal activities
- Occlusion rates at 6 months
- Comparison of the cost effectiveness of the intervention

Background

Varicose veins are common and are known to affect approximately one third of the population¹. Chronic venous disease (CVD) has been shown to have a negative impact on the quality of life of patients and treatment of varicose veins has been demonstrated to lead to improvement in the quality of life of patients²⁻⁴. Over the past decade, new endovenous techniques have been introduced and these are felt to be cost-effective, especially, when performed in an outpatient or 'office-based' setting⁵.

There is currently uncertainty about the use of compression stockings following treatment of varicose veins. In their consensus statement in 2008, the International Union of Phlebology (IUP) stated that there is good evidence for using compression in certain clinical indications⁶. These include the management of telangiectasia after sclerotherapy, varicose veins in pregnancy, prevention of thromboembolism and healing of ulcers. However, a few questions remain unanswered, such as the length of treatment and level of compression to be used⁶. The Society for Vascular Surgery and the American Venous Forum recommend using compression stockings post-operatively for 1 week to prevent haematoma formation, pain and swelling⁷. The 2013 NICE Guidelines on Varicose Veins in the Legs recommended the use of compression hosiery for no more than 7 days after interventional treatment for varicose veins⁸. However, due to current uncertainty of compression bandaging or hosiery compared to no compression after interventional treatment for varicose veins, the NICE Guideline Development Group have advocated further research to evaluate the clinical and cost effectiveness of this post-procedure intervention⁸. The guidelines also suggested looking into the length of time compression bandaging should be worn if it shown to be beneficial⁸.

Several researchers have looked into the practice of using compression after venous ablation. In a survey of the management of varicose veins by the members of the Vascular Society of Great Britain and Ireland, Edwards et al. found that the majority of surgeons used bandages post-operatively, with 49% using elastic bandages⁹. The literature on the use of compression stockings following treatment of varicose vein is limited.

Between December 2006 and February 2008, Bakker and colleagues conducted a prospective randomised controlled trial on the use of compression stockings after endovenous laser ablation of the great saphenous vein¹⁰. One hundred and nine patients were approached with 93 finally randomised to use compression stockings for 2 days (Group A) and 7 days (Group B), respectively. All patients were followed up for 3 months post-treatment and the visual analogue scale (VAS) for pain was recorded at 48 hours, 1 week and 6 weeks. A physical examination and quality of life was assessed at 1 week and 6 weeks. Occlusion rate at the 3 month point was also evaluated. Physical function and vitality was shown to be significantly better in group B at 1 week follow-up, but there was no statistically significant difference at 6 weeks. At 1 week, it was also noted that the VAS score in group B (VAS score 2.0 ± 1.1) was significantly lower than in patients wearing compression stockings for 48 hours (VAS score 3.7 ± 2.1) ($p \leq 0.001$)¹⁰. No significant difference was, however, observed at 6 weeks post-procedure. Limitations of the study include the high drop out of the trial (40 out of the initial 109 approached) and the absence of any phlebectomies or sclerotherapy in the patients.

Elderman et al. carried out a randomised trial to assess the effect of compression stockings after endovenous laser therapy (EVLT) for great saphenous vein incompetence¹¹. Patients' reported pain scores and quality of life scores was evaluated on the day of the procedure, 2-3 days afterwards and 2-6 weeks post-procedure. A total of 111 patients were randomised to stockings (n=55) and no

stockings (n=56). There was a statistically significant difference in the pain scores in favour of the stockings group up to day 7, but this difference was no longer present by week 6. There was also a greater use of analgesia in patients in the no stockings group compared to patients wearing stockings ($p < 0.05$). In addition, patients wearing stockings reported a statistically significantly higher score of satisfaction at 2 days (4.44 vs 4.15) and at 6 weeks (4.59 vs 4.18). The absolute difference was, however, small. Two notable limitations of the study were the high level of drop outs (16 from each group) and the absence of any blinding.

Hamel-Desnos et al. undertook a randomised controlled trial looking at the effect of compression in patients receiving foam sclerotherapy of the saphenous vein¹². They noted that patients with compression had similar pain and quality of life scores to patients not wearing any compression. They concluded that additional use of compression had no impact on the effectiveness of obliteration of veins, satisfaction scores, symptoms and quality of life, and that further controlled trials were needed to answer the question of whether using compression results in any difference to the outcome of varicose vein procedures.

We, therefore, propose to undertake a multicentre randomised study looking at the effect of compression therapy after endovenous thermal ablation.

Description

This will be a multicentre randomised clinical trial looking at the impact of wearing or not wearing compression stocking following endothermal ablation (either endovenous laser treatment (EVLT) or radiofrequency ablation (RFA)) of incompetent truncal veins. **If clinically indicated, patients will receive adjuvant treatment (e.g., concurrent phlebectomies or foam injection).**

Patients will be randomised **to** group A (compression) and group B (no compression). Only the use of compression will be randomised while the decision as to which treatment to use will be at the discretion of the clinical team.

Target Population

Patients referred for treatment of symptomatic varicose veins will be recruited if they are found to have primary great saphenous (GSV) or small saphenous vein (SSV) incompetence on colour duplex scan.

Inclusion Criteria

- Adults over 18 years of age
- Symptomatic GSV or SSV vein reflux **>** 0.5 seconds on colour Duplex
- **Recurrent varicose veins (if suitable for endothermal treatment)**

Exclusion Criteria

- Current DVT

- Arterial disease (ABPI<0.8)
- Vein diameter < 3mm
- Patient who are unwilling to participate
- Inability or unwillingness to complete questionnaires

Intervention

Patients will be randomised to have compression (group A) or no compression (group B). The compression therapy used will be Class II compression stockings. The treatment offered will be endothermal ablation (either endovenous laser treatment (EVLT) or radiofrequency ablation (RFA)) of incompetent truncal veins. Adjuvant treatment to tributaries (e.g., concurrent phlebectomy or foam sclerotherapy) will be carried out, if indicated.

Patients randomised to group A will be asked to wear compression stockings for 1 week.

Patients randomised to group B and undergoing endothermal ablation only will not be provided with any compression. However, if they receive adjuvant treatment to their tributaries, they will be provided with bandages to wear for 24 hours only, with no further compression afterwards.

At baseline, patients will be asked to fill quality of life questionnaires (EQ-5D, AVVQ and CIVIQ) and will have their clinical scores assessed (CEAP and VCSS). On discharge after their varicose vein intervention, they will then be provided with a diary to record their post-procedural pain every day for 10 days using a validated visual analogue scale (VAS) as well as to record when they return to their normal activities and are back to work. They will also be asked to attend a follow-up in 2 weeks and at 6 months.

Patients' GP will also be sent a letter to inform them of their patient's participation in the study.

Follow-up

Patients will be followed up in the outpatient clinic at 2 weeks and 6 months.

Follow-up at 2 Weeks

At the 2 weeks' follow-up, the diary containing details of the pain scores and how soon patients were able to return to normal activities/work will be collected. In addition, patients will be asked about any bruising or phlebitis they have had in the two weeks after their procedure and how compliant they have been with the compression. They will be examined and the Venous Clinical Severity Score (VCSS) will be recorded. They will also be asked to fill in the EQ-5D, AVVQ and CIVIQ scores.

Follow-up at 6 Months

At the 6 months follow-up, patients will be examined and their VCSS will be recorded. They will also be asked to fill the EQ-5D, AVVQ and the CIVIQ scores. They will have a venous Duplex scan to determine occlusion of the treated vein.

Sample Size and Study Duration

We estimated the sample size needed to observe a difference of at least 10mm in the VAS score, with a standard deviation of 20mm. With power at 90% and 5% significance equivalence, we would need to recruit 174 patients (87 per group).

Previous studies looking at compression stockings have shown drop out rates close to 37% at 3 months¹⁰. Therefore, if we estimate a drop out rate of about 50% by 6 months, we would need to recruit at least 348 patients. If we recruit at least 7 patients per week, this will be approximately a total of 364 patients that could potentially be randomised over the year. With 6 months follow-up, therefore, the study will be running for 18 months with a target recruitment of 350 patients.

Settings

Two hospital trusts in London will be recruiting patients for the study. These will be the:

1. Imperial College NHS Trust
2. North West London Hospitals NHS Trust

ETHICAL ARRANGEMENTS

Ethical approval will be sought from a Regional Research Ethics Committee as per the National Research Ethics Service. Patients will be screened by [name] (or another research fellow), who is also members of the direct care team, and patients thought eligible will be provided with information material about the trial and varicose veins and its treatments.

They will be invited to attend for their varicose vein procedures another day and will have until then to consider their participation into the trial (more than 24 hours to consider).

On the day of their procedure, they will be asked by [name] (or another research fellow) to confirm their consent by providing a written consent prior to participating in the trial.

The National Health Service (NHS) Trust Research and Development approval will also be sought prior to starting the trial.

DATA HANDLING & DISSEMINATION OF RESULTS

All patient data will be anonymised and stored on a password protected access database under the guidelines of the Data Protection Act 1998. Patient records will be kept on paper in the form of the diary card questionnaires and clinical scoring sheets. These will be kept in a locked filing cabinet at the and stored at the Charing Cross Hospital for 10 years in accordance with the Imperial College Trust Policy.

Data and study findings will be presented locally within the hospital, as well as national and international peer reviewed presentations and peer-reviewed journals.

Criteria for Electively Stopping the Trial or Other Research Prematurely

The trial may be stopped prematurely due to loss of equipoise or any major adverse effect as a result of treatment in any of the treatment arms.

Adverse events

No significant adverse events are expected.

Adverse Event (AE): any untoward medical occurrence in a patient or clinical study subject.

Serious Adverse Event (SAE): any untoward and unexpected medical occurrence or effect that:

- **Results in death**
- **Is life-threatening** – *refers to an event in which the subject was at risk of death at the time of the event; it does not refer to an event which hypothetically might have caused death if it were more severe*
- **Requires hospitalisation, or prolongation of existing inpatients' hospitalisation**
- **Results in persistent or significant disability or incapacity**
- **Is a congenital anomaly or birth defect**

REPORTING PROCEDURES

All adverse events should be reported.

Depending on the nature of the event the reporting procedures below should be followed.

Any questions concerning adverse event reporting should be directed to the Chief Investigator in the first instance.

Adverse Events (AE)

All such events, whether expected or not, should be recorded.

Serious Adverse Events (SAE)

An SAE form should be completed and faxed to the Chief Investigator within 24 hours.

All SAEs should be reported to the Research Ethical Committee where in the opinion of the Chief Investigator, the event was:

- 'related', ie resulted from the administration of any of the research procedures; and
- 'unexpected', ie an event that is not listed in the protocol as an expected occurrence

Reports of related and unexpected SAEs should be submitted within 15 days of the Chief Investigator becoming aware of the event, using the NRES SAE form for non-IMP studies.

Local investigators should report any SAEs as required by their Local Research Ethics Committee, Sponsor and/or Research & Development Office.

In the event of any harm to participants in the trial, Imperial College holds Public Liability (“negligent harm”) and Clinical Trial (“non-negligent harm”) insurance policies which apply to this trial.

ETHICS APPROVAL

The Chief Investigator has obtained approval from the **National Research Ethics Service (NRES) Committee - London (Fulham)**. The REC reference is **15/LO/0181**. The study protocol will be submitted for Site Specific Assessment (SSA) at each participating NHS Trust. The Chief Investigator will require a copy of the Trust R&D approval letter before accepting participants into the study. The study will be conducted in accordance with the recommendations for physicians involved in research on human subjects adopted by the 18th World Medical Assembly, Helsinki 1964 and later revisions.

CONSENT

Consent to enter the study will be sought from each participant only after a full explanation has been given, an information leaflet offered and time allowed for consideration. Signed participant consent will be obtained. The right of the participant to refuse to participate without giving reasons will be respected. After the participant has entered the study the clinician remains free to give alternative treatment to that specified in the protocol at any stage if he/she feels it is in the participant’s best interest, but the reasons for doing so will be recorded. In these cases the participants remain within the study for the purposes of follow-up and data analysis. All participants are free to withdraw at any time from the protocol treatment without giving reasons and without prejudicing further treatment.

CONFIDENTIALITY

The Chief Investigator will preserve the confidentiality of participants taking part in the study and is registered under the Data Protection Act.

INDEMNITY

Imperial College London holds negligent harm and non-negligent harm insurance policies which apply to this study.

SPONSOR

Imperial College London act as the main Sponsor for this study. Delegated responsibilities will be assigned to the NHS trusts taking part in this study.

FUNDING

There are no funders for this study.

AUDITS

The study may be subject to inspection and audit by Imperial College London under their remit as sponsor and other regulatory bodies to ensure adherence to GCP and the NHS Research Governance Framework for Health and Social Care (2nd edition).

Reference:

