Appendix 2: Aberdeen Varicose Vein Questionnaire

[figure not shown]
YOUR VARICOSE VEINS

1. Please draw in your varicose veins in the diagram(s) below:-

Legs viewed
from front

Legs viewed
from back

2. In the last two weeks, for how many days did your varicose veins cause you pain or ache?

(Please tick one box for each leg)

	R Leg	L Leg
None at all		
Between 1 and 5 days		
Between 6 and 10 days		
For more than 10 days		

3. During the last two weeks, on how many days did you take painkilling tablets for your varicose veins?

(Please tick one box for each leg)

	R Leg	L Leg
None at all		
Between 1 and 5 days		
Between 6 and 10 days		
For more than 10 days		

- 4. In the last two weeks, how much ankle swelling have you had?**
(Please tick one box)
- | | | |
|--|--------------------------|--|
| None at all |  | |
| Slight ankle swelling |  | |
| Moderate ankle swelling (eg. causing you to sit with your feet up whenever possible) |  | |
| Severe ankle swelling (eg. causing you difficulty putting on your shoes) |  | |
-
- 5. In the last two weeks, have you worn support stockings or tights?**
(Please tick one box for each leg)
- | | R Leg | L Leg |
|--|--------------------------|--------------------------|
| No |  |  |
| Yes, those I bought myself without a doctor's prescription |  |  |
| Yes, those my doctor prescribed for me which I wear occasionally |  |  |
| Yes, those my doctor prescribed for me which I wear every day |  |  |
-
- 6. In the last two weeks, have you had any itching in association with your varicose veins?**
(Please tick one box for each leg)
- | | R Leg | L Leg |
|-------------------------------|--------------------------|--------------------------|
| No |  |  |

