Appendix 6: Venous Clinical Severity Score (VCSS)

Please indicate right or left leg or bilateral (R, L or B)

	Absent	Mild	Moderate	Severe
Pain	None	Occasional, non/ no analgesia restricting	With moderate activity, occasional analgesia	Daily, severe limitations, regular analgesia
Varicose veins>4mm	None	Few	Multiple GSV	Extensive GSV and LSV
Venous oedema	None	Evening/ankle	Afternoon/ above knee	Morning/requiring elevation
Skin pigmentation	None	Limited and old/brown	Diffuse lower third/ purple	Wide/ purple
Inflammation	None	Mild cellulitis in marginal area	Moderate involving most of gaiter area	Severe cellulitis or significant eczema
Induration	None	Focal <5cm	Medial or lateral less than lower 1/3	1/3 of lower leg or more
Number of active ulcers	0	1	2	3
Active ulcer duration	None	<3 months	>3 months <12 months	>12 months
Active ulcer diameter(cm)	None	<2	2-6	>6
Compression	Not used or non compliant	Intermittent use	Stockings worn most days	Stockings worn daily
Total				

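### The VCSS total and the AVVQ both count stocking use, so trial-issued stockings can worsen Group A's 2-week scores without any difference in disease, and the plan has no rule for this

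*Combined protocol and SAP*

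**What the plan says.** The Secondary Objective list names two between-group comparisons that matter here: "The clinical change using the VCSS at baseline, 2 weeks and 6 months" and "The quality of life scores at baseline, 2 weeks and 6 months using the EQ-5D, AVVQ and CIVIQ scores". The Follow-up at 2 Weeks section confirms that both the VCSS and the AVVQ are collected at that visit.

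The VCSS form in Appendix 6 has ten rows above its total. One of them is Compression. Its Absent column reads "Not used or non compliant" and its Severe column reads "Stockings worn daily", so more stocking use means a worse score. The form prints no period over which use is to be judged.

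Question 5 of the AVVQ in Appendix 2 asks: "In the last two weeks, have you worn support stockings or tights". The answers run from no to prescribed stockings worn every day. No item weights are printed.

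The Intervention section sets the exposure. For the compression arm: "Patients randomised to group A will be asked to wear compression stockings for 1 week". Group B receives no stockings, but if tributaries are treated "they will be provided with bandages to wear for 24 hours only, with no further compression afterwards". At the 2-week visit patients are also asked "how compliant they have been with the compression".

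Nothing in the document tells assessors, patients or analysts how to treat either item when the trial itself supplied the stockings. There is no analysis section for the secondary outcomes.

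**The concern.** In routine care, stocking use can be read as a marker of disease burden, and both scales score it that way (for the AVVQ this is inferred from the order of the answers). In this trial, stocking use in Group A in the first week is the randomised treatment. Scoring it as severity puts allocation, and adherence to it, directly into the outcome. Randomisation gives no protection, because the imbalance arises after randomisation and as a result of it.

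The direction is against compression. The 2-week VCSS comparison could show harm that does not exist, or hide a real benefit, depending on how assessors read one row. With two hospital trusts recruiting and no instruction, the reading may also differ between assessors.

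**Working it through.** **The plan's own sample size.** Inputs from Sample Size and Study Duration: difference 10 mm, SD 20 mm, power 90%, significance 5%.
- Normal approximation, two-sided: n = 2 × (1.96 + 1.2816)² × (20/10)² = 84.1, so 85 per group.
- A t-test solution gives 85.03, so 86 per group. The stated 87 per group (174 in all) is close enough to count as reproduced.
- Drop-out: 174 / (1 − 0.50) = 348, as stated.
- The target of 350 is 175 per arm at equal allocation.

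This point disputes none of these figures. They only supply the arm sizes used below.

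**What the VCSS row can add at 2 weeks.** I assume columns scored 0 to 3, since the form prints no points. For a Group A patient who wore the stockings as asked:
- Scored on current use: 0, because stockings should have been off for about a week.
- Scored over the two weeks since the procedure: naturally the second category, intermittent use, so 1.
- Scored on the stocking week alone: up to 3.

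The mean shift is the share of Group A scored for trial stockings times the points given, less any points Group B receives for 24-hour bandages.

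**Chance of a false result against compression.** Assumptions: t-test on totals, no true difference, VCSS SD of 2, 3 or 4 points (the documents give none). The formula is

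P = Φ( shift / (SD × √(2/n)) − 1.96 ).

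Example: n = 87, SD 2, shift 0.5. The standard error is 2 × √(2/87) = 0.303; 0.5/0.303 = 1.65; Φ(1.65 − 1.96) = 0.378.

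| Per arm | Mean shift | SD 2 | SD 3 | SD 4 |
|---|---|---|---|---|
| 87 | 0 | 2.5% | 2.5% | 2.5% |
| 87 | 0.2 | 10% | 6% | 5% |
| 87 | 0.5 | 38% | 19% | 13% |
| 87 | 1 | 91% | 59% | 38% |
| 175 | 0.5 | 65% | 34% | 21% |
| 175 | 1 | >99% | 88% | 65% |

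A noncentral t calculation agrees within 0.5 percentage points. If 70% of Group A score 1 point, simulation of 20,000 trials at 87 per arm gives 62%, 33% and 20% for SD 2, 3 and 4. The 87 per arm allows for 50% drop-out by 6 months; the 175 rows apply if nearly everyone attends at 2 weeks.

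**Chance of hiding a benefit.** With SD 3 and 87 per arm, a true 1-point benefit is detected with probability Φ(1/0.455 − 1.96) = 59%. A 0.5-point artefact leaves a net 0.5 points, and Φ(0.5/0.455 − 1.96) = 19%.

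**AVVQ.** The two-week window at a 2-week visit covers the stocking week. A Group A patient who complied and answers truthfully reports stocking wear; a Group B patient with no other stockings answers no. That later answers score worse is inferred from their order. The shift cannot be calculated without weights.

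**The case against.** The strongest reply concerns the VCSS. Stockings come off after a week, the score is taken at an examination a week later, and most other rows describe present state. Read the same way, the Compression row is 0 in both arms and there is no artefact. Compliance is asked about separately, so it need not feed the VCSS. A score of 3 would require the assessor to consider only a week that has already ended.

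That reading is possible but the form does not force it. The row's categories are frequencies of use, which need a period, and none is given. The row itself refers to non-compliance, and compliance is discussed at the same visit. The current-use reading also does nothing for the AVVQ, whose window is printed. It is fair, though, that the AVVQ's prescribed-stocking answers are in the present tense and sit awkwardly with stockings already stopped.

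A second reply is that the sizes rest on assumed SDs and shifts. That stands. Partial misreading may be the likelier case: if 20% of Group A score 1 point, the chance is only 5–10%. A mean shift of 1 needs, for example, every Group A patient to score 1 or a third to score 3.

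A third is that no secondary outcome has analysis rules, so this is one gap among many. That is true, but an ordinary analysis section would not close it, because a correctly run test on full totals would still carry the artefact.

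**Conclusion.** The concern holds and should be fixed. The forms establish the mechanism, and no rule deals with it. Its size on the VCSS is uncertain: nil if assessors score current use, and large enough to produce or mask a significant difference if many score the trial stockings. The percentages depend on 0–3 scoring, SDs of 2 to 4 and the stated mean shifts, none of which the documents supply. The AVVQ effect rests on firmer timing, but its size is unknown and its direction is inferred.

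The scope is limited to two secondary outcomes at one visit. The primary pain outcome and its sample size are not affected by this route, nor are the 6-month scores if stockings stop as planned. Stocking use before the procedure may enter the baseline scores, but randomisation should balance that.

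**What to change.** - Pre-specify that between-group comparisons involving the 2-week visit use the VCSS total without the Compression row (nine items; maximum 27 instead of 30 under 0–3 scoring) and the AVVQ total without Question 5.
- Rescore baseline on the same reduced item set, and 6 months as well in any change-score or longitudinal model, so that scales are not mixed.
- Report the full totals at every visit as supplementary results.
- State on the VCSS form which period the Compression row covers.
- Use the two removed items as compliance and contamination data, alongside the diary and the compliance question.

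This costs some analysis-plan wording and one line on a form. The forms already collect the items, so no extra patients or visits are needed. The drawback is that reduced totals are not directly comparable with published totals, which the supplementary full totals cover. A period statement on the VCSS form alone would reduce assessor variation but would leave the AVVQ item untouched.

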Appendix 9. Patient Diary

Please indicate at what stage you were able to return to work and your normal daily activities (the activities you were able to do prior to treatment).

Please also indicate the day when you stopped wearing the compression stockings (if provided).

(Please tick one box)

	Day I was able to resume my normal activities	Day I returned to work	Day I stopped wearing compression stockings (if provided)
Day of surgery			
Day after surgery			
2 days after surgery			
3 days after surgery			
4 days after surgery			
5 days after surgery			
6 days after surgery			
7 days after surgery			
8 days after surgery			
9 days after surgery			
10 days after surgery			
>10 days after surgery			

Please return to:

[name]
Academic Department of Vascular Surgery
[name]
Charing Cross Hospital
[name]
London
[name]
[contact]

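### A secondary objective compares the severity of bruising and phlebitis at two visits, but the schedule specifies no grading at either visit and no collection at the later one

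*Combined protocol and SAP*

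**What the plan says.** Under Objectives, Secondary Objective, the two groups are to be compared on "The degree of bruising and phlebitis at 2 weeks and 6 months".

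Under Follow-up at 2 Weeks, "patients will be asked about any bruising or phlebitis they have had in the two weeks after their procedure". The same visit includes an examination, for which one score is named: "They will be examined and the Venous Clinical Severity Score (VCSS) will be recorded".

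Under Follow-up at 6 Months there are three elements:
- Clinical: "At the 6 months follow-up, patients will be examined and their VCSS will be recorded".
- Questionnaires: the same three quality-of-life instruments as at the earlier visit.
- Imaging, limited to whether the vein has closed: "They will have a venous Duplex scan to determine occlusion of the treated vein".

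Neither bruising nor phlebitis is mentioned in that section.

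**The concern.** The objective fixes a construct (degree) and two time points. The schedule specifies no measure of that construct, and it covers only one of the time points. Two sites that follow it could each record something different, or nothing beyond the patient's answer. Severity and 6-month status that were never recorded cannot be recovered at the analysis stage. The trial would then have to drop a stated secondary outcome or define it after the data are in, which invites a charge of selective reporting.

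The outcome is not peripheral. The Background reports that two specialist societies recommend stockings after treatment partly to limit haematoma, so bruising is an outcome readers will look for.

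**Working it through.** **1. Objective against schedule.** The objective needs four cells.

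| Outcome | Visit | Collection specified | Degree specified |
|---|---|---|---|
| Bruising | 2 weeks | Ungraded patient question | No |
| Phlebitis | 2 weeks | Ungraded patient question | No |
| Bruising | 6 months | None | No |
| Phlebitis | 6 months | None | No |

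Collection is specified in 2 of 4 cells and degree in 0 of 4.

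**2. Could a form fill the gap?**
- VCSS (Appendix 6): no bruising or phlebitis row. The nearest are skin pigmentation and inflammation, and the latter is graded by cellulitis and eczema (its lowest positive level is "Mild cellulitis in marginal area").
- AVVQ (Appendix 2): the nearest item concerns purple discolouration from small skin vessels, which is not bruising.
- EQ-5D (Appendix 1), CIVIQ-14 (Appendix 8), the clinical assessment sheets (Appendices 4 and 5) and CEAP (Appendix 7): no such item.
- Diary (Appendix 9): opens with "Please indicate at what stage you were able to return to work and your normal daily activities" and adds only the day stockings were stopped. Appendix 10 records pain only.

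**3. Numbers available.** The protocol gives no figure for this outcome. Its only sample size is for the VAS: 2 × (1.960 + 1.282)² × 20² / 10² = 84.1, so 85 per group against the stated 87, which is close. Then 174 / (1 − 0.50) = 348, as stated. The target of 350 gives 175 per group before losses. With the planned 50% loss, 350 × 0.50 = 175 patients in total would remain at 6 months.

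**4. What grading would be worth at 2 weeks.** The documents give no bruising or phlebitis rate, so these inputs are assumptions: none/mild/moderate/severe percentages in the more affected arm, a common odds ratio of 1.8 towards milder grades in the other arm, a two-sided 5% test, and 175 per group with no loss by 2 weeks.

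Graded outcome: power = Φ( √[ n (ln OR)² (1 − Σp̄³) / 6 ] − 1.96 ), where p̄ is the mean proportion in each grade.

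Yes/no outcome: power = Φ( [ |p₁ − p₂| √n − 1.96 √(2 p̄ (1 − p̄)) ] / √[ p₁(1 − p₁) + p₂(1 − p₂) ] ), where p is the proportion with none.

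Worked case, 20/30/30/20%:
- The cumulative odds 0.25, 1 and 4 become 0.45, 1.8 and 7.2, so the other arm is 31.0/33.3/23.5/12.2%.
- Σp̄³ = 0.0716 and (ln 1.8)² = 0.3455.
- Graded: √(175 × 0.3455 × 0.9284 / 6) = 3.06; 3.06 − 1.96 = 1.10; power 86%.
- Yes/no: (0.1103 × 13.23 − 1.96 × 0.617) / 0.612 = 0.41; power 66%.

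The same steps give the other rows. Simulation (Mann-Whitney against chi-square) agrees within two points.

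| None/mild/moderate/severe, % | None in other arm, % | Σp̄³ | Formula, graded v yes/no | Simulation, graded v yes/no |
|---|---|---|---|---|
| 20/30/30/20 | 31.0 | 0.0716 | 86% v 66% | 87% v 66% |
| 50/30/15/5 | 64.3 | 0.2076 | 81% v 77% | 80% v 77% |
| 70/20/7/3 | 80.8 | 0.4332 | 67% v 65% | 65% v 64% |

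With 87 per group instead of 175, the first row falls to about 58% v 39%.

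**The case against.** Several points on the other side have force.

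- **The 2-week question need not be yes/no.** Asking about any bruising does not forbid recording how bad it was. A reader might infer that a binary item is specified. The text supports only that no grading method is specified. An ungraded comparison of occurrence within two weeks also remains possible.
- **Six months need not be empty.** Patients are examined then, and the adverse-event section asks for every event to be recorded. A reader might infer that no information at all would exist, but phlebitis could be caught by these routes. They would still not give a graded comparison at a fixed time.
- **Some material is not in the supplied text.** It passes from Appendix 2 to Appendix 4, the Appendix 11 flowchart has a heading only, and the data-handling section mentions clinical scoring sheets. A grading form cannot be excluded. The body of the protocol refers to none for these outcomes.
- **The power gain is conditional.** A reader might infer that grading always improves power substantially. That holds when most patients are affected. The gain is small with half unaffected and about one point with 70% unaffected. The documents do not say which applies, and bruising and phlebitis may differ.
- **Limiting haematoma is not the protocol's own rationale.** The Background attributes it to the societies' recommendation, while the protocol's own position is that the benefit of compression is uncertain.

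These points limit what can be claimed. They do not remove the mismatch between objective and schedule.

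**Conclusion.** The point holds as a mismatch between a stated secondary objective and the schedule meant to deliver it. As written, no measure of degree is specified at either visit and no collection of bruising or phlebitis is specified at 6 months, so the comparison named in the objective cannot be made. This rests on the supplied text alone and needs none of the power figures. It assumes that Appendix 3 and the flowchart contain no grading item.

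The statistical value of grading runs from about 21 percentage points of power (87% v 66%) to about 1 (65% v 64%), under an assumed odds ratio of 1.8, 175 per group and the three assumed distributions.

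This is one of seven secondary objectives. A reader might infer that the trial's main result is threatened. It is not, because the primary pain outcome and its sample size do not depend on this item. The change is worth making before recruitment because unrecorded data cannot be repaired later.

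**What to change.** At 2 weeks, keep the recall question, because it covers the whole fortnight and an examination shows only what is present that day. Add two separate items to the existing examination form, one for bruising and one for phlebitis. Each should be scored none/mild/moderate/severe, with the extent of each level defined and the same scale used at both sites. State that arms will be compared with an ordinal method, for example a proportional-odds model or a Mann-Whitney test, separately for each outcome.

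At 6 months, either add the same two items to the existing examination form or delete that time point from the objective. If Appendix 3 or the flowchart already holds a grading form, cite it in both follow-up sections instead.

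The cost is a few tick-box lines, or a wording change for 6 months, with no new visit. The drawback is that the protocol describes no blinding, so a clinician's score is open to assessor bias unless the assessor is unaware of allocation. The plan should say which will apply.
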